9.3. Un-blinding Procedures

The investigator should follow the trial's randomization procedures and should ensure that the code is broken only in accordance with the protocol. The treating investigator should promptly document and explain to the St. Jude Principal Investigator (PI) any premature un-blinding of the investigational agent (e.g., accidental un-blinding, or un-blinding due to a serious adverse event). The study PI determines the attribution and grading of Adverse Events as well as decides, in sponsor-investigator trials, if breaking of a study blind is necessary. In deciding, the St. Jude PI may consider:

- Are there any specific antidotes for the investigational agent or blinded chemotherapy agent(s),
- Are drug-drug interactions expected that may preclude medical intervention,
- Would discontinuation of IND or blinded agent(s) be likely to have an immediate effect?

- Participant and data management

It is recommended that, when possible and appropriate, the blind be maintained for those persons responsible for analysis and interpretation of results at the study's conclusion.

Any toxicities associated or possibly associated with study treatment should be managed according to standard medical practice.

- Accidental Un-blinding

In the event of accidental un-blinding by study personnel, the following should occur:

- Information on accidental un-blinding (including subject number, person(s) involved, information shared, whether the un-blinded person has patient contact) is sent to the St. Jude site Principal Investigator (PI).
- The St. Jude PI provides a summary of the incident to the Biostatistician and the un-blinded study clinical research monitor.
- The protocol deviation will be recorded in a blinded manner and communicated to the primary blinded monitor.
- Blinded site staff will be re-trained by the blinded MONITOR, and un-blinded site staff will be retrained by the un-blinded MONITOR on procedures for maintaining the blind. A summary of the issue and the re-

training will be documented in both the blinded monitoring visit report and the un-blinded monitoring visit report.

- Monitors will ensure appropriate actions are taken (e.g., that the affected study participant is treated according to protocol specifications concerning un-blinding, that a corrective action to prevent unintentional un-blinding is implemented, that the event is recorded in the deviation log in a blinded manner, and that the SMC or other appropriate parties were notified or consulted as applicable)

- Emergency Un-blinding

In cases of patient safety (medical emergency or serious medical condition), the treating physician may request un-blinding a participant randomization code, if knowledge of the treatment assignment is essential for the clinical management or welfare of the participant. Un-blinding of treatment assignment prior to documented disease progression is permitted only for a serious, un-expected adverse event suspected to be study drug-related (as part of the safety reporting process) and if necessary for patient management.

Procedure for Requesting Un-blinding of a Unique Participant Identifier or Randomization Code:

- The study St. Jude PI is the only one who has authority to approve for un-blinding a participant randomization code or identification code.
- In a medical emergency, every effort should be made to consult with the St. Jude PI (insert PI emergency contact phone number) to discuss other options prior to requesting un-blinding of a participant randomization code.
- The treating physician at St. Jude shall make a request to the St. Jude PI.
- The treating physician may hold administration of the investigational agent while waiting for a decision on un-blinding to be made.
- The St. Jude PI may consult with Investigational Pharmacy for un-blinding, if applicable.
- The St. Jude PI will contact the investigational pharmacist to provide the randomization code for the individual participant.
- The un-blinding information for the participant should be limited to as few individuals as possible. The blinded study team and the participant should remain blinded.
- Documentation of the incident will be maintained in the pharmacy binder. All documents associated with the incident should be recorded in a

blinded manner in the EMR and/or other documents, such as, emails, if the participant remains on study and the data will be included in study data analysis.

- If the un-blinding was due to an adverse event, confirm the adverse event was reported and documented in accordance with applicable reporting procedures and timelines.

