- suggests that the research places subjects or others at a greater risk of harm (including physical, psychological, economic, or social harm) than was previously known or recognized. An unanticipated problem involving risk to subjects or others may exist even when actual harm does not occur to any participant.

Consistent with FDA and OHRP guidance on reporting unanticipated problems and adverse events to IRBs, the St. Jude IRB does not require the submission of external events, for example IND safety reports, nor is a summary of such events/reports required; however, if an event giving rise to an IND safety or other external event report constitutes an “unanticipated problem involving risks to subjects or others” it must be reported in accordance with this policy. In general, to be reportable external events need to have implications for the conduct of the study (for example, requiring a significant and usually safety-related change in the protocol and/or informed consent form).

Although some adverse events will qualify as unanticipated problems involving risks to subjects or others, some will not; and there may be other unanticipated problems that go beyond the definitions of serious and/or unexpected adverse events. Examples of unanticipated problems involving risks to subjects or others include:

- Improperly staging a participant’s tumor resulting in the participant being assigned to an incorrect arm of the research study;
- The theft of a research computer containing confidential subject information (breach of confidentiality); and
- The contamination of a study drug. Unanticipated problems generally will warrant consideration of substantive changes in the research protocol or informed consent process/document or other corrective actions in order to protect the safety, welfare, or rights of subjects or others.

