9.2. Recording Adverse Events and Serious Adverse Events

Adverse events associated with the influenza virus vaccine will not be recorded for this study. Other adverse events will be graded using the Division of Microbiology and Infectious Diseases (DMID) Pediatric Toxicity Tables (Appendix III). All grades of these events will be recorded.

Adverse events will be collected from enrollment through the participant's last visit. Any AE that has not had a stop date recorded by the participant's last visit will continue to be followed-up until an outcome or resolution has occurred. Study participants will be instructed to notify study personnel at any time during the study if they are hospitalized or have any unusual, alarming or unexpected events.

Adverse events will be assessed by the investigator for severity, relationship to the study product, possible etiologies and whether the event meets criteria as a serious adverse event.

The following guidelines will be used by investigators to assess the relationship of an AE to study product administration:

- Definite: Unquestionable relationship. The event was directly attributable to the study product.
- Probable: Relationship is likely. It is likely that the study product caused the event.
- Possible: Relationship may exist. There is at least a reasonable possibility that the event was caused by the study product, although the likelihood is low.
- Unlikely: Relationship is not likely. Although it is unlikely that the study product caused this event, causality cannot be entirely ruled out.
- Unrelated: No relationship. The study product did not cause the event.

Factors considered in assessing the relationship of an AE to study product include:

- the temporal relationship of the event to the administration of study product;
- whether an alternative etiology has been identified; and
- biological plausibility.

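### The approval rule for emergency un-blinding in Section 9.3 depends on disease progression, which cannot occur as a defined event in healthy children, so its narrow restriction never lifts

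*Combined protocol and SAP*

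**What the plan says.** The Emergency Un-blinding part of Section 9.3 opens with two consecutive sentences.

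- The first covers emergencies and serious conditions. In these, "the treating physician may request un-blinding a participant randomization code, if knowledge of the treatment assignment is essential for the clinical management or welfare". It sets no test of causality or expectedness.
- The second reads "Un-blinding of treatment assignment prior to documented disease progression is permitted only for a serious, un-expected adverse event suspected to be study drug-related" and ends with a further condition: "suspected to be study drug-related (as part of the safety reporting process) and if necessary for patient management".

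On authority, the procedure says: "The study St. Jude PI is the only one who has authority to approve for un-blinding a participant randomization code or identification code". Earlier in 9.3 the PI is the person who "decides, in sponsor-investigator trials, if breaking of a study blind is necessary", with a short list of matters that may be considered (antidotes, drug interactions, the effect of stopping the agent). The same section tells the investigator to make sure the code is broken only as the protocol allows.

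Sections 2.2 and 4.1 describe the participants as healthy volunteers and healthy children. Section 8.1 lists the off-study criteria.

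**The concern.** The second sentence is the only one that says when un-blinding is permitted, and its time limit is disease progression. That limit makes sense in a treatment trial, where the restriction falls away once the disease has progressed. Here nothing can end it. What remains is a permanent rule that the event must be serious, unexpected and suspected to be related to the product, and that the code must also be needed for management.

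At stake is a child in an emergency whose physician needs to know whether vitamins or placebo were given, for an event that fails one of those tests. The first sentence invites the request and the second, as written, bars its approval.

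**Working it through.** No arithmetic applies and the plan gives no figure to reproduce. The check compares the two sentences and then looks for any event that could end the restriction.

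**Step 1. Is there a progression event?** The term *disease progression* occurs once in the document, in this sentence. None of the six off-study criteria in 8.1 is a progression event (completion, influenza infection or anti-influenza medication, death, loss to follow-up, participant or parent request, PI discretion). Influenza infection comes nearest, but it is not called progression and is not linked to un-blinding. Section 9.1 mentions the natural progression of an underlying disease, but only inside a general definition of an unexpected event. It sets no study milestone. The set of participants past documented progression is therefore empty, and the restriction covers everyone throughout.

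**Step 2. Conditions side by side.**

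- Sentence 1 (request): emergency or serious condition AND assignment essential to care or welfare.
- Sentence 2 (permission): serious AND unexpected AND suspected related AND needed for management.

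| Case | Sentence 1: may be requested | Sentence 2: permitted |
|---|---|---|
| Serious, unexpected, suspected related; assignment essential | Yes | Yes |
| Serious, expected, suspected related; assignment essential | Yes | No |
| Serious, not suspected related; assignment essential | Yes | No |
| Serious, unexpected, suspected related; needed for safety reporting but not for care | No | No |

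Rows 2 and 3 are the defect. Row 4 shows that the word *and* makes management an added condition, so safety reporting is not a route of its own.

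**Step 3. Could rows 2 and 3 arise?** Two hypothetical cases show that they could.

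- A child swallows vitamins at home. The event might be judged unrelated to the study product, yet knowing whether a high-dose study gummy had also been given could matter to care.
- A recognised vitamin A toxicity might be classed as expected under the 9.1 definition, which turns on whether the study documents already describe the event.

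**Step 4. Does another provision cover the gap?** Toxicities associated or possibly associated with study treatment are to be managed by standard practice, and the physician may hold product while awaiting a decision. The first limits harm. The second helps little: there are only two supervised doses, on Days 0 and 28, so nothing is left to hold after Day 28.

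**The case against.** The strongest reply is that the sentences are two steps of one rule: a broad right to ask, then a narrower test for approval. This stands as a reading, and it answers a stronger claim that a reader might make, namely that 9.3 leaves the PI with no rule on which sentence governs. On the two-step reading the second sentence governs approval. That does not cure the defect. It means the approval test requires refusal of some requests where the assignment is essential to the child's welfare.

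A second reply is that the PI has discretion and a list of clinical considerations not confined to unexpected, related events. The list does give guidance, but it does not remove the word *only*, and 9.3 requires the code to be broken in accordance with the protocol.

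A third is that the gap is nearly empty. If the gummy is not suspected, the assignment will seldom be essential. If it is suspected, the event will usually be unexpected, because 2.2 states that the vitamin A dose is below doses linked to toxicity. This largely stands as a statement about frequency, although that sentence in 2.2 does not cover the vitamin D3 in the same gummy. It does not make the rule right for the case that does occur.

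It can also be argued that the clause is plainly inapplicable here, or covers only safety-reporting un-blinding. Either may be what was intended, but the text selects neither.

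**Conclusion.** The point holds as a minor wording defect in a participant-safety rule. Read literally, the approval sentence applies to every child at all times and is narrower than the care-based criterion just before it. Affected cases should be rare, and the documents give no rate from which to estimate them. No power, sample size or efficacy result changes. The conclusion rests on reading *only* and *and* in their ordinary sense, and on there being no progression event defined anywhere in the document.

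Three further inferences are not supported:

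- **A numerical size.** A reader might count levels of the five-level attribution scale in 9.2 that fall below suspected. That counts labels, not events. The boundary is also undefined, since the *Unlikely* level itself says: "Although it is unlikely that the study product caused this event, causality cannot be entirely ruled out".
- **Proven oncology carry-over.** The chemotherapy wording in 9.3 and the example in 9.1 of mis-staging a "tumor resulting in the participant being assigned to an incorrect arm of the research study" make an un-adapted template likely, but origin remains an inference and the defect does not depend on it.
- **No emergency contact.** The unfilled telephone placeholder in 9.3 does not show that no number exists.

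**What to change.** Replace the disease-progression sentence with wording such as: *With PI approval, the blind may be broken when knowing the assignment is essential to the participant's care or welfare or, separately, when safety reporting of a serious, unexpected event suspected to be related to study product requires it.*

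Replacement is better than deletion, because the present sentence holds the only mention, within the emergency procedure, of un-blinding for safety reporting.

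The cost is a wording amendment to 9.3 with the IRB review that 12.1 requires for protocol modifications. It adds no visits, samples, staff or participants. Filling in the telephone placeholder, removing the chemotherapy wording and using one description of the treating physician throughout 9.3 are optional clean-up for the same edit and are not part of this point.

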10.0 DATA COLLECTION, STUDY MONITORING, AND CONFIDENTIALITY

10.1. Data Collection

All study data will be collected by the study staff using designated source documents. Data will be entered and maintained in an institutional relational database with separate backup and monthly off site backup. Standard GCP practices will be followed to ensure accurate, reliable and consistent data collection.

10.2. Study Monitoring

The study team will hold monthly meetings and review case histories or quality summaries on participants.

Source document verification of eligibility and informed consent for 100% of St. Jude participants will be performed by the Eligibility Coordinators within 5 working days of completion of enrollment.

The Clinical Research Monitor will perform monitoring of applicable essential regulatory documentation. Also, reviewing for the timeliness of serious adverse event reporting (type, grade, attribution, duration, timeliness and appropriateness) for selected study participants *semi-annually* and track accrual continuously. The monitor will verify those data points relating to the primary study objective for a certain number of study enrollees as specified in the Moderate Risk monitoring plan checklist for this study. Protocol compliance monitoring will include participant status, safety assessments, eligibility, the informed consent process, participant protocol status, off-study, and off-therapy criteria. The Monitor will generate a formal report which is shared with the Principal Investigator (PI), study team and the Internal Monitoring Committee (IMC).

Monitoring may be conducted more frequently if deemed necessary by the CPDMO or the IMC.

Continuing reviews by the IRB and CT-SRC will occur at least annually. In addition, SAE reports in TRACKS (Total Research and Knowledge System) are reviewed in a timely manner by the IRB/ OHSP.

10.3. Confidentiality

All study procedures will be conducted in private, and every effort will be made to protect participant privacy and confidentiality to the extent possible.

Data collection, process, and administrative forms, laboratory specimens, and other reports will be identified by a coded number only to maintain participant confidentiality. The study database will identify study participants only by the study identification number and will not contain personal health or other identifiers. The list containing the study number and personal identifiers will be maintained in a secured file indefinitely. All study-related information will be stored securely. All participant information will be stored in locked file cabinets in areas with access limited to study staff. All records that contain names or other personal identifiers, such as locator forms and informed consent forms, will be stored separately from study records identified by code number. Databases will be secured with password-protected access systems. Participants' study information will not be released without their written permission, except as necessary for monitoring. Personal identifiers will not be included in any study reports.

All study records will be kept confidential to the extent provided by national and local laws. Authorized representatives of the sponsor(s), and regulatory agencies may examine (and when required by applicable law, to copy) study records for the purposes of quality assurance reviews, audits and evaluation of the study safety and progress.

11.0 STATISTICAL CONSIDERATIONS

11.1. Anticipated Completion Dates

Anticipated Primary Completion Date: 24 months following enrollment of the first participant.

Anticipated Study Completion Date 5 years following approval of the

protocol

11.2. Sample Size

The primary goal of the study is to estimate the effect size of vaccination when incorporating vitamin A/D supplements and standard care. The primary endpoint of interest will be the proportion of 4X increases or conversion from an undetectable to a detectable response in virus-specific antibody after two immunizations (compared to the starting titer) in intervention and control groups. We plan to enroll 40 participants per group in total. Assuming an attrition rate of about 5%, approximately 38 vaccine plus vitamin and 38 vaccine plus placebo participants will provide data for the primary objectives. Because this is a pilot study and there is very limited information about vitamin supplementation with influenza vaccination among children, the sample size was chosen based on past experience with clinical trials of other respiratory virus vaccines among a pediatric population at SJCRH and published literature (39). The sample size proposed will suffice for capturing the response rate difference between groups with a power of over 80% at a significance level of 5%, if the true average response rate overall with the Vitamin A/D supplements is over 62% (EAST 6) while the response rate in the vaccine only group is 30% on average, the majority of the enrolled participants are either vitamin A or D or both deficient as suggested by our experience. If the effect size is smaller, we still believe the estimated effect size with the proposed 80 participants will inform future larger studies.

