11.4. Summary of Primary and Secondary Objectives

For all analyses, all continuous titer measures will be log transformed unless otherwise specified

Analysis of Primary Objectives

In Section 4.1, we have described a way to equally assign enrolled siblings into two arms. By doing this, ignoring the possible nonindependence in siblings when obtaining group difference should still provide a consistent estimate of the group difference. The precision (i.e., the width of the 95% confidence interval) of the estimate may be inflated, while the degree of inflation of the precision depends on the number of co-enrolled siblings, which is not predictable at this stage. Given the fact that this study is a pilot study, we believe in the value of obtaining an accurate group difference estimate, and allow some leeway in precision. More precise estimates and more power could be achieved through future larger studies.

To assess the vaccine-induced and total antibody (IgG and IgA) response and IgA/IgG plus IgA/IgM ratios in the sera at days 28 and 56.

The serum antibody response described by the proportion of 4X increases or conversion from undetectable to detectable response in virus-specific antibody after two immunizations in intervention and control groups will be estimated and 95% confidence interval will be described for both groups, overall and by stratum. The proportion difference with 95% confidence interval will be reported, overall and by stratum. Due to possible variation in virus strains and the influenza virus vaccine formula in different flu seasons, analyses by season will also be described. Continuous titer values in both groups, overall or by stratum, will also be described and compared with point estimate along with 95% confidence intervals.

Titer ratios, such as IgA/IgG and IgA/IgM will be summarized with descriptive statistics, including mean, standard deviation, median and range, for each intervention group, overall or by season. Two-sample tests (t-test or Wilcoxon rank-sum test) will be applied whenever appropriate.

We will also apply generalized estimating equations (GEE) or mixed models to explore titer levels longitudinally.

As sensitivity analysis, similar analytic procedures will be additionally implemented by treating 4X increases or conversion from undetectable to detectable response in virus-specific antibody after two immunizations as an endpoint.

Analysis of Secondary Objectives

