To assess the functional antibody response toward the influenza virus vaccine in the sera

Secondary analyses will examine sero-conversion defined as antibody HAI titers of $<1:20$ converting to $\geq 1:20$, or a four-fold increase in titer for participants with a starting titer of $\geq 1:20$. Sero-conversion rate will be estimated with proportion and 95% confidence interval for both groups, overall and by stratum. The rate difference will be described with point estimate and 95% confidence interval, overall and by stratum. Due to possible variation in virus strains and influenza virus vaccine compositions in different flu seasons, analyses by season will also be described.

Continuous titer values in both groups, overall or by stratum, will also be described and compared with point estimate along with 95% confidence intervals.

We will also apply generalized estimating equations (GEE) or mixed models to explore titer levels longitudinally.

Analysis of Exploratory Objectives

To describe the socio-demographic characteristics and nutritional diet among children participating in the trial.

Socio-demographic and dietary intake will be described with tables and descriptive statistics (frequency, proportion mean, standard deviation, median, range, etc...). The anticipated socio-demographic heterogeneity of participants may preclude further analysis, but if feasible, relationships between socio-demographic characteristics and dietary intake with outcomes will be examined.

To assess the feasibility of the food diary among healthy volunteers as measured by completion of the diary.

To assess the feasibility of the food diary among healthy volunteers, the proportion and 95% confidence interval of participants who complete and return the food diary will be calculated overall and at each visit time point.

To monitor serum Vitamin A and D levels at various time points.

Serum Vitamin A and D levels at screening, days 0, 28 and 56 will be monitored, plotted and described at each time point. Summary statistics, such as mean, standard deviation, median and range, will be provided for all time points. If feasible, paired comparisons and longitudinal modeling will be explored.

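### The continuous titer comparison that accompanies the responder endpoint makes no stated use of the starting titer; it should be pre-specified as a baseline-adjusted log titer or log fold rise

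*Combined protocol and SAP*

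**What the plan says.** Section 11.2 defines the primary endpoint: "The primary endpoint of interest will be the proportion of 4X increases or conversion from an undetectable to a detectable response in virus-specific antibody", judged after two immunizations against the starting titer. The only power statement in the plan belongs to this endpoint. It claims a comparison "with a power of over 80% at a significance level of 5"% when the supplement arm responds at more than 62%, "while the response rate in the vaccine only group is 30% on average". Planned size: "We plan to enroll 40 participants per group in total", with about 38 per arm left after 5% attrition. The same section calls the trial a pilot whose goal is to estimate the effect size.

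Section 11.4 log-transforms continuous titers and then says: "Continuous titer values in both groups, overall or by stratum, will also be described and compared with point estimate along with 95% confidence intervals". It adds GEE or mixed models to explore titers over time, without stating their terms or the contrast of interest. The sensitivity analysis listed there names the same 4X-or-conversion endpoint again, so it does not test the effect of the cut.

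The functional antibody endpoint follows the same pattern: "Secondary analyses will examine sero-conversion defined as antibody HAI titers of" below 1:20 reaching at least 1:20, or a four-fold rise from a higher start. It is followed by the same sentence on continuous titer values and the same exploratory models.

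**The concern.** Children start from different titers, and the question is how far vaccination with or without the supplement raises them. The responder endpoint uses the starting titer but reduces the rise to yes or no. The continuous comparison keeps the full scale but, as written, may be carried out on post-vaccination values alone, with baseline differences between children left in the error. Either way, information that the trial collects may not be used.

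At stake is the precision of the estimate handed to the larger trial. With about 38 children per arm that estimate is already imprecise, and 11.2 itself allows that the true effect may be smaller than planned for.

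**Working it through.** **Inputs.** From 11.2: p0 = 0.30, p1 = 0.62, n = 38 per arm, alpha 5%. Sidedness is not stated; two-sided is assumed. The documents give no mean, SD or distribution for titers, so everything after step 1 rests on stated assumptions.

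**1. The plan's own figure.** Pooled two-proportion z-test, mean rate (0.30 + 0.62)/2 = 0.46:
- SE under no difference = sqrt(2 × 0.46 × 0.54 / 38) = 0.1143
- SE under the alternative = sqrt((0.30 × 0.70 + 0.62 × 0.38) / 38) = 0.1083
- power = Φ((0.32 − 1.96 × 0.1143) / 0.1083) = Φ(0.886) = 81.2%

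Exact enumeration of the same test gives 81.4%; Fisher's exact test gives 74.5%. The claim of over 80% reproduces. With 40 per arm the pooled figure is 83.2%.

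**2. Log rise, normal with equal SD (assumed).** The implied shift is z(0.62) − z(0.30) = 0.305 + 0.524 = 0.830 SD. The noncentrality is 0.830 × sqrt(38/2) = 3.617. Two-sample t-test power is 94.6% (normal approximation 95.1%). The gap to the exact responder figure is 94.6 − 81.4 = 13.2 points.

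**3. Other shapes, with the responder rates held at 30% and 62% (simulated, 38 per arm; the responder test stays at about 81-82%).**

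| Shape of the log rise | t-test | Wilcoxon |
|---|---|---|
| SD ratio (intervention/control) 0.5 | 96% | 94% |
| SD ratio 2 | 87-88% | 85% |
| Two-fold steps, floor at no rise | 90-92% | 91% |
| Logistic | 89% | 91% |
| Heavy tails (t, 3 df) | 69% | 87% |
| Responder/non-responder mixtures | 75-78% | 72-76% |

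Further simulations used the plan's exact responder rule, two-fold dilutions and an assay floor. They assumed 0-60% of children undetectable at baseline and an SD of the log2 rise of 1.5 to 2.5. The log fold rise had about 87-95% power.

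**4. Day 56 titers without baseline.** Suppose the rise is normal and independent of the starting titer. The Day 56 log titer then has SD sqrt(sB² + sR²), where sB is the baseline SD and sR the SD of the rise. The standardized shift falls to 0.830 × sR / sqrt(sB² + sR²). With sB = 1.5 log2 (assumed):
- sR = 1.5: shift 0.587, power Φ(0.587 × 4.359 − 1.96) = 73%
- sR = 2.0: shift 0.664, power 82-83%
- sR = 2.5: shift 0.712, power 87%

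A wider baseline spread is worse: sB = 2.5 with sR = 1.5 gives a shift of 0.427 and 46% power. Simulations with dilutions and a floor gave 73-87% in one set of assumptions and 46-88% in another. In the first set, the log rise or a baseline-adjusted comparison had 91-95%. Once the baseline SD exceeds about three quarters of the SD of the rise (1.5 against 2.0 above), the unadjusted continuous comparison is no better than the responder test.

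**The case against.** **The 95% is not the plan's number.** A reader might infer that the cut costs 13 points under the plan's own assumed rates. The documents do not support that. The rates fix only the 81%; the 95% needs a normal, equal-SD rise. Under mixtures the responder test does better by about 3 to 6 points. The plan assumes no shape, and its mouse data point both ways: after priming only supplemented animals responded, while after the booster titers were higher in the supplemented group (section 2.2). This objection stands.

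**The responder rate is a defensible primary.** Section 2.1 describes vaccine performance as the share of children who respond, and the 30% is in that unit. Conversion from undetectable has a censored baseline, which the responder rule handles and a fold rise does not without an imputed value. A reader might infer that the endpoint must be replaced; in a pilot aimed at estimation, reasonable statisticians would differ. This stands too.

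**Continuous analyses are already planned.** A reader might infer that nothing in the plan recovers the lost information. That is too strong: an arm-by-time contrast in the mixed model would compare rises. But the model is exploratory and no such contrast is specified, and the one stated between-arm continuous comparison is of titer values. The objection weakens the point without removing it.

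**Power matters less in a pilot.** 11.4 accepts some loss of precision because of siblings, and no go/no-go test is defined. The figures are therefore best read as measures of precision. That does not justify leaving out a baseline that is already collected.

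**Conclusion.** The concern holds in a limited form. The primary and only powered endpoint is a responder proportion cut from a measured titer, and its stated power is correct. The gap is in the accompanying continuous comparison, for virus-specific antibody and for HAI, which does not say that it uses the starting titer.

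Using the starting titer brings power to about 87-95% under graded effects with realistic assay features, against about 46-88% for Day 56 values alone and about 81% for the responder test. These ranges rest on assumed SDs, baseline spread and undetectable fractions. If the supplement acts as an all-or-none switch, the advantage over the responder test disappears or reverses. That is a reason to report both estimates rather than to replace one with the other.

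**What to change.** In 11.4, define the continuous between-arm comparison as the log2 titer at Day 56 adjusted for the starting log2 titer and RBP stratum (or the log2 fold rise, adjusted for stratum). Report it as a ratio of geometric means or of geometric mean fold rises with a 95% CI, for virus-specific antibody and for HAI.

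State which sample supplies the starting titer, since 6.1 and 6.2 list immunologic serum at both Screening and Day 0. Give undetectable titers a fixed value, such as half the lowest dilution, and add a rank-based or censored-data check.

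Present this beside the responder difference as a pre-specified key estimate for the larger trial. The responder proportion may stay primary; promoting the fold rise to sole primary is optional.

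The cost is wording only, because the samples, assays and log transformation are already planned. The small downside is the need to agree a convention for undetectable titers before the data are seen.
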